In this study, patients with progressive keratoconus receives a single dose of the ophthalmic solution RitSight™ (CE0477) delivered into the cornea manually for at least 15 minutes and treated by using the C4V CHROMO4VIS™ system with the theranostic software module while they are observed and tested for a period of 12 months after treatment to assess correlation between the theranostic imaging biomarker and the K_{max} flattening.

Follow-up for each participant is twelve months after treatment. The interval is long enough to observe treatment efficacy as well as any effect or complication induced by the innovative corneal cross-linking procedure performed by using the theranostic UV-A medical device in a participant.

Study Participants

The inclusion criteria are: diagnosis of progressive keratoconus. Participants with 18-40 years old are eligible, all genders.

According to the most recent scientific literature⁹, the criterion to determine progression of keratoconus is based on providing at least one of the following types of evidence:

- at least two Placido disk corneal topography measurements showing at least +1.00 D steepening of the K_{max} value in the last year or longer interval period.
- at least two central corneal thickness (CCT) measurements showing at least -10 µm change in in the last year or longer interval period.

⁹ Ferdi A, et al. Keratoconus Natural Progression: A Systematic Review and Meta-analysis of 11 529 Eyes. Ophthalmology 2019;126:935-945

The exclusion criteria are: corneal apex steeper than 63 D, corneal thickness thinner than 400 µm; corneal scarring; descemetocèle; history of herpetic keratitis; concomitant eye diseases; inflammatory eye diseases; glaucoma; cataract; nistagmus; pregnancy; breast feeding.

The study does not accept healthy volunteers.

If both eyes of a participant are eligible, the eye with lower CDVA will be chosen as the study eye.

Study Arm

One study arm receiving either corneal cross-linking treatment after epithelial debridement (“Theranostic Epi-OFF CXL”) or transepithelial corneal cross-linking treatment (“Theranostic Epi-ON CXL”). Only one eye of each participant is designated as the study eye.

Discontinuation of contact lens wear

Participants must discontinue the use of contact lenses from seven days before baseline visit to 3 months follow-up; thereafter, they must discontinue the use of contact lenses at least seven days before the remaining follow-up visits at day-180 and day-360.

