Manifest Refraction	X	X	X	X	X	X	X
Corneal Topography/Pachymetry	X	X	X	X	X	X	X
Corneal Specular Microscopy	X	X	X	X	X	X	X
Slit Lamp Microscopy	X	X	X	X	X	X	X
Ocular Tonometry	X						X
Dilated fundus Examination	X						X
Theranostic data		X					
Adverse Events	X	X	X	X	X	X	X

Visit 1 – Baseline

Potential candidates will undergo a complete eye examination to determine their eligibility to the study. Before any test is conducted, the participants will be given a brief explanation of the study (including the number and time of visits to be performed).

The baseline visit will provide the confirmation that the participant is eligible for the inclusion in the study and the full medical history will be collected. Baseline measurements will be performed in the following order:

1. Corneal curvature and corneal thickness measurements using the computerized corneal topography device.
2. Endothelial cell density measurement using the specular microscopy.
3. Uncorrected Distance Visual Acuity, measured with ETDRS chart at a test distance of 4 m.
4. Corrected Distance Visual Acuity, measured with ETDRS chart at a test distance of 4 m.
5. Manifest Spherical Equivalent Refraction with ETDRS chart at a test distance of 4 m.
6. Slit lamp bio-microscopy of the ocular surface and the anterior segment of the eye.
7. Intra-ocular pressure (IOP) measurement.
8. Dilated fundus examination.

At the end of the baseline assessment, eligible participants shall the informed consent form (Annex 3) and will be assigned an individual stratification number according to the stratification protocol described in the corresponding section of this study protocol.

Participants will be also reminded to bring sunglasses the day of surgery.

Treatment (day 0)

Participants will receive theranostic-guided cross-linking treatment according to the RUO User Manual and the Investigator's Brochure instructions and the following section "Treatment".

After treatment, each participant will receive medical therapy and relative instructions (Annex 3).

NOTE: To provide standard medical care, the participants treated by EpiOFF theranostic-guided CXL will be visited at day 3 to discontinue the use of contact lens in the treated eye.

Visit 2, 3, 4 and 5 – Follow up (day 7, day 30, day 90 and day 180 respectively)

These visits will provide follow-up measurements, which will be performed in the following order:

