Synopsis on disposition of participants

Sample size

By expecting a response rate of 50% of cases that will reach the threshold of -1.05 D of the K_{max} value, a sample size of 42 patients achieves 91% power to detect a difference of 0,25 between the area under the ROC curve (AUC) under the null hypothesis of 0,60 and an AUC under the alternative hypothesis of 0,85 using a two-sided z-test at a significance level of 0,05000. The data are continuous responses. Considering a $\leq 20\%$ drop-out rate (determined from systematic literature review on controlled and open clinical studies on standard and epithelium-on CXL procedures), a number of 50 participants (25 per treatment protocol) is allowed to be enrolled in the study.

Details on the methodology and process used to define the sample size of this clinical trial are described in Appendix 1 – Methodology for sample size calculation.

Statistical methodology

Descriptive statistics will be used to summarize the data: numerical variables will be summarized as mean and standard deviation or median and interquartile range, respectively, according to the distribution of the data; categorical variables will be represented as frequencies and proportions. Student's t-test or Wilcoxon test will be applied to compare continuous variables, while Fisher's exact test or Chi-Squared test will be used to analyze categorical variables. Bonferroni correction is applied to analysis of exploratory outcome measures of stratification groups. For all reported AEs, the data can be presented with events listed in order of decreasing frequency.

The optimal cut-off values in predicting the propensity of CXL treatment to flatten the Kmax value at 12-months was determined based upon the results of preclinical studies (data not disclosed to investigators to avoiding methodological study bias) and can be optimized with the Youden index. The accuracy and precision (95% CI) of the combined use of the theranostic imaging biomarkers to predict CXL treatment outcome will be determined by calculating the proportion of correctly classified eyes and the positive predictive value (PPV) respectively. The miss rate, which is the probability that a true positive is missed by the theranostic methodology, will be determined by calculating the false negative rate (FNR).

Statistical significance will be set at 0.05. All the analysis will be performed using the statistical software R (latest version available).

Population to be analysed

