The Principal Investigator/Site of Investigation must document and explain in the participant's source documentation any deviation from the approved protocol. The Principal Investigator/Site of Investigation may implement a deviation from, or a change of, the protocol to eliminate an immediate hazard to trial participants without prior IEC approval. As soon as possible after such an occurrence, the implemented deviation or change, the reasons for it, and any proposed protocol amendment(s) should be submitted to the IEC for review and approval, to the sponsor for agreement, and to the regulatory authorities, if required.

A deviation from the protocol is an unintended and/or unanticipated departure from the procedures and/or processes approved by the Sponsor and the IEC and agreed to by the Principal Investigator/Site of Investigation. Deviations usually have an impact on individual participants or a small group of participants and do not involve inclusion/exclusion or primary endpoint criteria. A protocol violation occurs when there is nonadherence to the protocol that results in a significant, additional risk to the participant, when the participant or Principal Investigator/Site of Investigation has failed to adhere to significant protocol requirements (inclusion/exclusion criteria) and the participant was enrolled without prior sponsor approval, or when there is nonadherence to authorities regulations.

The Sponsor will document protocol violations and deviations throughout the course of monitoring visits. The Sponsor will notify the principal investigator during a visit and/or in writing of all violations and deviations. The IEC should be notified of all protocol violations and deviations in a timely manner.

List of major deviations/violation

- Patient not met inclusion criteria
- Patient not met exclusion criteria
- Not obtained signed consent form from patient
- Corneal topography not done at visit 1 (baseline)
- Corneal topography not done at visit 6 (day 360)
- Corneal cross-linking treatment not completed

Financial Disclosure and Obligations

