3. Soeters N et al. Transepithelial versus epithelium-off corneal cross-linking for the treatment of progressive keratoconus: a randomized controlled trial. *Am J Ophthalmol* 2015;159(5):821-8.e3.
4. Hashemian H et al. Evaluation of corneal changes after conventional versus accelerated corneal cross-linking: a randomized controlled trial. *J Refract Surg* 2014;30(12):837-42.
5. Lombardo M et al. Randomized controlled trial comparing transepithelial corneal cross-linking using iontophoresis with the Dresden protocol in progressive keratoconus. *Ophthalmology* 2017; 124: 804-812.
6. Al Fayed MF et al. Transepithelial versus epithelium-off corneal collagen cross-linking for progressive keratoconus: a prospective randomized controlled trial. *Cornea* 2015; 34 Suppl 10:S53-6.

The analysis of pertinent data from the above articles provided the following results:

- **354 cases** have been treated by standard corneal cross-linking showing an average K_{max} change of **-1.41 ± 1.71 D after 1 year follow-up**; the average K_{max} change was **-0.89 ± 0.60 D at 6-month follow-up**.
- **91 cases** have been treated by transepithelial corneal cross-linking showing an average K_{max} change of was **-0.32 ± 1.55 D after 1 year follow-up**; the average K_{max} change was **-0.52 ± 1.20 D at 6-month follow-up**.
- In **122 control, no treated cases**, the natural history of keratoconus progression has shown a mean change of K_{max} **$+0.89 \pm 2.70$ D during 1-year follow-up**; the average K_{max} change was **$+0.93 \pm 1.35$ D at 6-month follow-up**.

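### The reference Kmax for the 12-month change is not named, and the implied Visit 1 reading has no time limit before treatment

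*Combined protocol and SAP*

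**What the plan says.** The Primary outcome measure section classifies eyes by whether Kmax flattens by more than 0.1 D at 12 months. It sets 85% as the minimum for accuracy and precision in the Per Protocol population. It does not name the starting reading. The Data Analysis part of the Synopsis refers only to a preoperative value.

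Two pre-treatment readings are available. In the Study Visits table, the row "Corneal Topography/Pachymetry" is marked at Visit 1, at day 0 and at every follow-up visit. The text is less even: Outcome Measures and Assessments lists the examinations for baseline and follow-up only, and neither Treatment (day 0) nor Treatment describes a topography or its timing.

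Three things point to Visit 1 as the reference:
- It carries the baseline label.
- Outcome Measures and Assessments equates baseline with before treatment.
- The List of major deviations/violation includes "Corneal topography not done at visit 1 (baseline" and the day-360 topography, but not the day-0 one.

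Visit 1 also serves eligibility: "The baseline visit will provide the confirmation that the participant is eligible for the inclusion in the study". One route to eligibility, under Study Participants, is two or more topographies showing "at least +1.00 D steepening of the K_{max} value in the last year or longer interval period". Change in corneal thickness is another route and, in the Synopsis only, so is change in refraction.

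Each follow-up visit has a tolerance window (±21 working days for Visit 6). No window links Visit 1 to treatment. The four-month enrolment period limits recruitment at a site, not this gap.

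**The concern.** If the change is measured from Visit 1, it includes whatever the cornea does between Visit 1 and treatment. These are eyes enrolled because they are progressing, so average drift is towards steepening. It hides flattening and turns true responders into apparent non-responders. The cut is only 0.1 D, so little drift is needed.

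The scores are validated against this classification. Movement before treatment has nothing to do with riboflavin uptake or UV-A response, so it enters as error in the reference standard and counts against accuracy and precision. If the reference is simply left undefined, the position is no better: the choice between two readings could be made after the data are seen.

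**Working it through.** **Inputs from the documents**
- Responder cut: flattening of more than 0.1 D (Primary outcome measure).
- Untreated course: Appendix 1 reports that "the natural history of keratoconus progression has shown a mean change of K_{max" of +0.89 ± 2.70 D over one year in 122 cases. Background and State-of-the-Art rounds this to +0.9 D per year.
- Change after treatment (Appendix 1): -1.05 ± 0.80 D overall; -1.41 ± 1.71 D standard; -0.32 ± 1.55 D transepithelial.
- Number evaluated: 42 (Sample size).

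**Step 1: the plan's own figure.** The plan states that "a sample size of 42 patients achieves 91% power to detect a difference of 0,25 between the area under the ROC curve (AUC" values of 0.60 and 0.85, "using a two-sided z-test at a significance level of 0,05000". With 21 responders and 21 non-responders, power = Φ((0.25 - 1.96 × SE0)/SE1). The Hanley-McNeil variance gives 89.9% and the equal-SD binormal variance gives 92.7%. The stated 91% lies between them. The figure of 42 is therefore used as it stands.

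**Step 2: time for drift to reach the cut.** 0.1/0.89 × 365 = 41 days.

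**Step 3: drift and reclassification by gap.** Drift = 0.89 × days/365. Change from Visit 1 equals change from treatment plus drift. Under a normal model, the responder share is Φ((-0.1 + 1.05 - drift)/0.80). With no gap it is Φ(0.95/0.80) = 88.2%.

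| Gap (days) | Drift (D) | Responder share | Loss (points) | Eyes of 42 |
|---|---|---|---|---|
| 30 | 0.07 | 86.3% | 1.9 | 0.8 |
| 60 | 0.15 | 84.2% | 4.0 | 1.7 |
| 90 | 0.22 | 81.9% | 6.3 | 2.6 |
| 120 | 0.29 | 79.4% | 8.8 | 3.7 |

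**Step 4: other response distributions, 90-day gap.**
- Standard: 77.8% falls to 73.8%, a loss of 4.0 points (1.7 eyes of 42).
- Transepithelial: 55.6% falls to 50.0%, a loss of 5.6 points (2.4 eyes of 42).

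**Step 5: room for error.** 0.85 × 42 = 35.7, so 36 eyes must be correct and 6 may be wrong (36/42 = 85.7%; 35/42 = 83.3%). Two to three reclassified eyes equal a third to a half of that allowance.

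**Step 6: selection, the opposite bias.** Suppose Visit 1 supplies the later of two Kmax readings that qualify an eye. Its expected error is then (e²/S) × φ(a)/(1 - Φ(a)), with a = (1.00 - 0.89)/S. Here e is the SD of Kmax measurement error and S the SD of observed change. The documents do not give e, so 0.3, 0.5 and 0.8 D are assumed. With S = 1.35 D (the untreated 6-month SD in Appendix 1) the shift is 0.06, 0.16 and 0.40 D. With S = 2.70 D (the 12-month SD) it is 0.03, 0.08 and 0.20 D. The range straddles 0.1 D, so the documents cannot settle its size.

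**The case against.** The strongest reply is that nothing says Visit 1 is the reference. The deviation list may protect that reading only because eligibility and the 54.0 D stratum need it, and a site could properly use day 0. This stands: Visit 1 is an inference, and the documented defect is that the reference is unnamed.

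The effect may also be small. If treatment follows within a month, fewer than one eye in 42 changes class on the figures above, and the documents do not show that waits are longer. That stands too; they only fail to rule longer waits out.

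Drift and selection act in opposite directions and may partly cancel on average. They need not fall on the same eyes, however, and accuracy counts individual eyes, so a small net mean shift does not restore correct classification.

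Four stronger readings are tempting but not supported:
- *The reading that qualifies the eye is also the reference.* The criteria ask for at least two measurements and neither say nor exclude that Visit 1 is one of them. Eyes can also enter on thickness or, per the Synopsis, refraction.
- *Selection alone exceeds 0.1 D.* This depends on a measurement-error SD that the documents do not give, and applies only to eyes entering on Kmax with Visit 1 as the later reading.
- *Three months of drift could approach 0.47 D.* This projects the untreated 6-month change (+0.93 D) as a steady rate, equal to 1.86 D per year, which the 12-month figure of +0.89 D contradicts.
- *Visit 1 readings are distorted by recent contact-lens wear.* The protocol requires seven lens-free days before baseline, and Recruitment strategies allows contact before that visit. Non-compliance would have to be assumed.

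**Conclusion.** The concern holds as an undefined reference combined with an uncapped interval. At the plan's own yearly rate, average pre-treatment progression exceeds the responder cut after about 41 days. At 90 days it is about 0.22 D and moves roughly 4% to 6% of eyes across the cut, or 2 to 3 of 42 on the main assumption, against an allowance of 6 errors.

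This assumes steady progression through the year, normally distributed change, the quoted SDs describing individual eyes, and literature changes that represent change from treatment. The 90-day gap is an illustration, not a figure in the plan. A reclassified eye becomes an error only where the score would otherwise have been right, so the eye counts show exposure, not a forecast of failures. Selection on a high Visit 1 reading is a possible secondary bias in the opposite direction, of unknown size.

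**What to change.** Define the 12-month Kmax change, for both the primary classification and the secondary efficacy measure, from the day-0 topography already in the schedule. State that it is acquired before any eye drop or epithelial removal. A day-0 reading not used for eligibility removes the pre-treatment drift and, in expectation, the selection shift.

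Keep Visit 1 for eligibility and the 54.0 D stratum. Use it as the reference only where the day-0 reading is missing, say how many eyes that affects, and report the Visit 1-based result as a sensitivity analysis.

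Do not add a missing day-0 topography to the major deviations. Population to be analysed excludes eyes with major deviations from the Per Protocol population, where the 85% criterion is judged, so the addition would drop those eyes and defeat the fallback.

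The cost is wording in the outcome, day-0 and analysis sections, with no extra test. The downside is that topography must come before eye preparation on the day of treatment. This fits the sequence under Treatment, where the operator enters corneal thickness and Kmax before the eye is prepared. Eyes on the fallback keep any drift.

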This study aims to validate the theranostic imaging biomarkers by assessing the change of maximum keratometry (K_{max}) after corneal cross-linking treatment (CXL). Based upon a systematic literature review, the study hypothesis is that CXL treatment can averagely flattening the K_{max} value by -1.05 D (SD: ± 0.80 D) at 1-year after CXL. To this scope, expecting a response rate of 50% of cases that will reach the threshold of -1.05 D of the K_{max} value, a sample size of 42 patients achieves 91% power to detect a difference of 0,2500 between the area under the ROC curve (AUC) under the null hypothesis of 0,6000 and an AUC under the alternative hypothesis of 0,8500 using a two-sided z-test at a significance level of 0,05000. Considering a $\leq 20\%$ drop-out rate (determined from

systematic literature review on controlled and open clinical studies on standard and epithelium-on CXL procedures), a number of 50 participants (25 per treatment protocol) is allowed to be enrolled in the study.

Products' description

The test articles to use in this study include two CE marked medical devices, such as the investigational one, herein the C4V CHROMO4VIS™ (CE1936) and the 0.22% riboflavin ophthalmic solution, herein the RitSight™ eye drop (CE0477), which must be applied onto the cornea before UV-A irradiation to protect the internal ocular structures from excessive UV-A light radiation.

The C4V CHROMO4VIS™ is a CE marked class IIb electronic UV-A medical device, which delivers ultraviolet light (365 nm wavelength) in a circular area onto the cornea. It is a portable system with articulating arm to allow movement of the system for alignment of the UV-A beam onto the patient's cornea. UV irradiance and irradiation time at the cornea are controlled by an onboard computer system. The medical device is equipped with the theranostic software (for research purpose only) that is the object of validation in this study. The RitSight™ is a CE marked sterile class IIa medical device consisting of a 0.22% riboflavin enriched solution for effective penetration of riboflavin into the corneal tissue to protect the inner ocular structures during UV-A irradiation.

Treatment

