Corneal cross-linking is performed with either the corneal epithelium intact or de-epithelialized in patients with progressive keratoconus. The ophthalmic solution *RitSight*™ is applied onto the cornea and its concentration into the cornea monitored by C4V CHROMO4VIS™ system with theranostic software module (v. 2.0). After the pre-set time for application of riboflavin onto the cornea is ended (i.e., 15 min. for epi-off CXL and 20 min. for epi-on CXL protocol), the cornea is illuminated by the C4V CHROMO4VIS™ system using 5.4 J/cm² UV-A energy dose (10 mW/cm² for 9 minutes).

Primary End Point and Outcome Measure

Time point 12 months: validation of the theranostic imaging biomarkers.

Validation of the combined use of the theranostic imaging biomarkers. True positives, false positives, true negatives and false negatives were evaluated in order to determine the ability of the theranostic imaging biomarkers, including both the *riboflavin score* and *theranostic score*, to predict the propensity of CXL treatment in flattening the K_{\max} value (D) by more than 0.1 D at 12 months postoperatively. True positives, false positives, true negatives and false negatives will be evaluated.

Secondary Outcome Measures

- Efficacy: Change of Maximum Keratometry (K_{\max}) assessed by corneal topography at 12-months.
- Safety: change of Endothelial Cell Density (ECD) assessed by specular microscopy at 12-months.

Exploratory Outcome Measures

- Change of Uncorrected Distance Visual Acuity (UDVA) assessed by ETDRS at 12-months.
- Change of Corrected Distance Visual Acuity (CDVA) assessed by ETDRS at 12-months.
- Change of Manifest Refraction assessed by ETDRS at 12-months.
- Change of primary and secondary outcome measures in either stratification group at 12-months.

Adverse events

Any adverse event (AE) occurring in a participant enrolled into the clinical trial shall be reported in detail on the CRF according to the ICH Guidelines and the MDCG 2020-10-2 Guidance safety report form. The Medical Dictionary for Regulatory Activities (MedDRA®) is used to code all AEs.

Study Records/Source Documents/Personal Data protection

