Adequate records (*Case Report Forms*) will be maintained for the study including subject medical and surgical records, test reports, signed informed forms, and information about subject discontinuation. All original documentation will remain at the investigative sites. Study data that are generated electronically (e.g. corneal topography etc.) will be printed and retained in the study files. A unique identifier will be assigned by the Investigators to each trial subject to protect the subject's identity.

Dropouts/Lost-to-follow-up/withdrawal

Participants may drop out at any time during the study. Based on the scientific literature and considered the 1-year follow-up, a ≤20% dropout may be expected in the study. A total number of 50 participants is therefore allowed to be enrolled in the study.

Statistical Methods

Descriptive statistics will be used to summarize the data: numerical variables will be summarized as mean and standard deviation or median and interquartile range, respectively, according to the distribution of the data; categorical variables will be represented as frequencies and proportions. Student's t-test or Wilcoxon test will be applied to compare continuous variables, while Fisher's exact test or Chi-Squared test will be used to analyze categorical variables. ROC curve analysis will be used to evaluate cut-off values for the theranostic imaging biomarker scores in predicting the propensity of CXL treatment to flatten the K_{max} value at 12-months. The cut-off value for the biomarker scores will be determined by optimizing the Youden index. Moreover, sensitivity, specificity, proportion of correctly classified eyes and positive predictive value (PPV) positive predictive values (PPV) and false negative rate (FNR) and confidence intervals will be calculated. The study set a minimum threshold of 85% for the theranostic software module's accuracy and precision in predicting the propensity of CXL to halt disease progression (intended as more than 0.1 D K_{max} flattening) at 1 year in the study population (per protocol population).

Statistical significance will be set at 0.05. All the analysis will be performed using the statistical software R (latest version available).

Data Analysis

Data will be summarized using descriptive statistics and graphical presentations.

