- Measurement of **corneal endothelial cell density** (ECD) with specular microscopy will assess will assess changes of the ECD after treatment.
- **Slit lamp biomicroscopy** will assess integrity of the cornea and anterior segment of the eye.

Primary outcome measure

Validation of the Theranostic Imaging Biomarker [Time Frame: 12-months]

- Validation of the combined use of the theranostic imaging biomarkers. True positives, false positives, true negatives and false negatives were evaluated in order to determine the ability of the theranostic imaging biomarkers, including both the *riboflavin score* and *theranostic score*, to predict the propensity of CXL treatment in flattening the K_{max} value (D) by more than 0.1 D at 12 months postoperatively.

Theranostics: confirmation of the theranostic imaging biomarker will be provided at the end of treatment procedure. The theranostic data, which will be recorded during treatment procedure, will be exported to a computer for subsequent analysis with 12-months data.

The accuracy and precision (95% CI) of the combined use of the theranostic imaging biomarkers to predict CXL treatment outcome were determined by calculating the proportion of correctly classified eyes and the positive predictive value (PPV) respectively. The miss rate, which is the probability that a true positive is missed by the theranostic methodology, was determined by calculating the false negative rate (FNR).

The study sets a minimum threshold of 85% for the theranostic software module's accuracy and precision in predicting the propensity of CXL to halt disease progression (intended as more than 0.1 D Kmax flattening) at 1 year in the study population, who participated and completed at least 66% of all the visits (i.e., 4 of 6 total visits) and the last at 12 months (i.e., Per Protocol Population);

Secondary outcome measures

Efficacy [Time Frame: 12-months]

- Change of Maximum Keratometry index assessed by corneal topography at 12-months.

Corneal topography: measurement of maximum simulated keratometry (K_{max} , D) will be done by using Placido disk corneal topography. The investigator will record the K_{max} value at each visit and will fill the corresponding CRF. This test is performed to provide evidence of corneal curvature change after treatment.

Safety [Time Frame: 12-months]

- Change of Endothelial Cell Density assessed by specular microscopy at 12-months.

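### The stated 91% power is for an AUC test at a -1.05 D cut; the primary endpoint's 85% minimum for accuracy and PPV has no pass probability or expected confidence-interval width

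*Combined protocol and SAP*

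**What the plan says.** **Sizing.** The Sample size section under Statistical Considerations starts from this premise: "By expecting a response rate of 50% of cases that will reach the threshold of -1.05 D". It concludes that "a sample size of 42 patients achieves 91% power to detect a difference of 0,25 between the area under the ROC curve (AUC"), with a null AUC of 0.60, an alternative of 0.85 and a two-sided z-test at 0.05. Fifty participants are to be enrolled, allowing for dropout of up to 20%. The Synopsis repeats this and adds the literature basis, that treatment flattens the Kmax "value by -1.05 D (SD: ± 0.80 D) at 1-year after CXL".

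**Primary endpoint.** The Synopsis, the Primary outcome measure section and the Final Report requirements all define the event as flattening "by more than 0.1 D at 12 months postoperatively", judged from true and false positives and negatives.

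**Success criterion.** Synopsis, Statistical Methods: "The study set a minimum threshold of 85% for the theranostic software" module's accuracy and precision, "at 1 year in the study population (per protocol population"). The Primary outcome measure section repeats the 85% minimum. Accuracy means the proportion of eyes correctly classified; precision means the PPV.

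**Analysis.** Statistical methodology: "The accuracy and precision (95% CI) of the combined use of the theranostic imaging biomarkers to predict CXL treatment outcome will be determined" from those two quantities. In the methods, ROC analysis serves only to evaluate cut-offs. No test of AUC against 0.60 is described.

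**The concern.** The sizing and the primary endpoint differ in three ways: the event (-1.05 D or more than 0.1 D), the statistic (AUC, or accuracy and PPV) and the criterion (rejecting 0.60, or reaching 85%). A reader who takes 91% as the chance that the study meets its primary objective is misled, because nothing in the plan gives that chance.

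The decision rule is also incomplete. A 95% interval will be reported, but its role against the 85% is not stated. The study supports conformity assessment, and the final report must reach a clear conclusion on this endpoint. A result such as 36/42, with an interval reaching down to 71%, could be argued either way after the data are seen.

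**Working it through.** **1. Reproduce the plan's figure.** Inputs from Sample size: 42 eyes, 50% responders (21/21), AUC 0.60 and 0.85, two-sided 0.05. The Hanley-McNeil variance with m responders and n non-responders is

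Var(A) = [A(1-A) + (m-1)(a-A²) + (n-1)(b-A²)]/(mn), with a = A/(2-A) and b = 2A²/(1+A).

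- A = 0.60: a = 0.4286, b = 0.4500; Var = (0.24 + 20×0.0686 + 20×0.0900)/441 = 0.00774; SE = 0.0880.
- A = 0.85: a = 0.7391, b = 0.7811; Var = (0.1275 + 20×0.0166 + 20×0.0586)/441 = 0.00370; SE = 0.0608.
- Power = Φ[(0.25 - 1.96×0.0880)/0.0608] = Φ(1.276) = 89.9%.

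This is close to 91%. The figure is sound for the test it describes.

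**2. Responder rate at each cut.** Inputs from Appendix 1, randomised trials at 1 year: standard -1.41 ± 1.71 D, transepithelial -0.32 ± 1.55 D. Normality is assumed.

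| Cut | Standard | Transepithelial | 1:1 mix |
|---|---|---|---|
| -1.05 D | Φ(0.36/1.71) = 58.3% | Φ(-0.73/1.55) = 31.9% | 45.1% |
| -0.1 D | Φ(1.31/1.71) = 77.8% | Φ(0.22/1.55) = 55.6% | 66.7% |

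The planned 50% is reasonable at -1.05 D. At 0.1 D the same sources give about 67%.

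**3. Effect of the changed cut on the AUC test.** Suppose AUC 0.85 carried over to 0.1 D (an assumption). With 28 responders and 14 non-responders the SEs are 0.0912 and 0.0584, so power = Φ(1.219) = 88.9%. The cut alone barely moves the figure.

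**4. The 85% rule for accuracy, with cut-offs fixed in advance.** The plan gives no true accuracy, so a range is assumed.

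*Point estimate must reach 85%.* With 42 eyes, 0.85×42 = 35.7, so 36 must be correct; the exact (Clopper-Pearson) 95% CI at 36/42 is 71.5-94.6%. With 40 eyes (50 less 20%), 34 must be correct; the CI at 34/40 is 70.2-94.3%. Exact binomial probability of passing:

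| True accuracy | 42 eyes | 40 eyes |
|---|---|---|
| 85% | 55% | 61% |
| 88% | 77% | 80% |
| 90% | 88% | 90% |

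The 40-eye figures are slightly higher only because 34/40 is exactly 85%, while 36/42 is 85.7%.

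*Lower 95% limit must reach 85%.* With 42 eyes, 41 must be correct (lower limit 87.4% at 41, 83.8% at 40). The probability is 7% at true accuracy 90% and 37% at 95%.

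**5. PPV.** The denominator is the number of positive calls, which the plan does not predict. With 28 (an assumption), the point estimate needs 24/28 (95% CI 67-96%) and passes 86% of the time at a true PPV of 90%. The probability of meeting both criteria cannot exceed the smaller of the two.

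**6. Direction of the cut-off assumption.** Statistical methodology says the cut-offs came from preclinical work but may be optimised with the Youden index; the Synopsis says they will be determined that way. If they are tuned on the same eyes, apparent accuracy is optimistic and the pass probabilities in step 4 are too low.

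**The case against.** The best defence is that the 91% is correct for its test and that the 85% rule is clear enough: a minimum set on two named proportions, with an interval reported beside them, means the estimates. Both parts largely stand. The figure reproduces, and the text favours the point-estimate reading. What remains is that this reading is not stated, and that even under it the plan gives no pass probability or interval width.

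Four stronger readings are tempting and are not supported:

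- **That the study has only a 7% chance of success.** This needs the lower-limit rule, and no section attaches the 85% to a confidence limit.
- **That the changed cut ruins the power.** AUC power falls to about 49% only if 88% of eyes respond (37/5). That rate treats the pooled 0.80 D as a between-eye SD, whereas Appendix 1's trial SDs are 1.55 and 1.71 D. It also sits oddly with the background section's statement that the standard protocol is effective in almost 70%. At 70% responders (29/13) AUC power is still about 88%.
- **That an uninformative score would pass.** Calling every eye a responder reaches 36/42 about 78% of the time at 88% responders, but only about 0.5% at 67% and 1.5% at 70%.
- **That 42 eyes are too few.** Adequacy cannot be judged until the rule and the expected accuracy and PPV are stated.

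**Conclusion.** The point holds as a gap between the sizing and the primary endpoint, and should be fixed. The 91% is right for an AUC test that the methods do not contain, at a cut that no outcome uses. The main problem is that it is not the power of the 85% rule; the change from -1.05 D to 0.1 D matters little by itself at a plausible responder rate of 67-70%.

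On the natural point-estimate reading, the chance of passing on accuracy alone with 42 eyes is about 55% to 88% for true accuracy of 85% to 90%, and no higher once PPV is added. These figures rest on assumed true accuracies, independent eyes and cut-offs fixed in advance. The 67% rests on normality and on the Appendix 1 trial means and SDs.

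**What to change.** In both Sample size sections (Synopsis and Statistical Considerations):

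1. Stop presenting 91% as the power of the primary objective.
2. State the expected responder rate at more than 0.1 D, with the mean, SD and source behind it.
3. Say that the 85% minimum applies to the point estimates of accuracy and PPV, or to their lower 95% limits if that is intended.
4. Give the probability of meeting that rule under stated true accuracy and PPV, or the expected 95% CI widths with 40-42 eyes (about 71-95% at 36/42 and 70-94% at 34/40).
5. Delete the AUC power statement, or recompute it at the 0.1 D definition, label it supportive and add that AUC test to the methods.

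The cost is one paragraph reworded in two places, one sentence defining the rule, and one line in the methods if the AUC test stays. The rewording adds no patients. Its downside is that the figure stated for the primary endpoint will probably be less favourable than 91%.
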